2. Seven subjects from cohort 3 and 7 subjects from cohort 4 will be selected for mosquito-feeding. They will also be randomized 5:2 (ZIKV:placebo) to ensure the clinical team remains blinded to the treatment assignment.

Product Description: ZIKV-SJRP/2016-184 and ZIKV-Nicaragua/2016 were isolated directly from the serum of subjects who were diagnosed with uncomplicated Zika illness. Each virus will first be evaluated at a dose of 10² plaque-forming units (PFU). At each subcutaneous dose, the virus will first be evaluated in 7 subjects (5 will have received ZIKV, 2 will have received placebo). The remaining subjects in each dose cohort will be inoculated with the current dose or dose escalation will occur according to predetermined criteria.

Primary Study Objective: Identify a suitable strain of ZIKV for use in safety-assured CHIM studies by:

1. Determining the proportion of infected subjects who demonstrate clinical signs/symptoms of Zika infection (fever, rash, conjunctivitis, pruritis, myalgia, arthralgia, headache) by ZIKV strain and dose
2. Determining the quantity and duration of ZIKV in blood, urine, cervico-vaginal secretions, semen, and saliva by culture (infectious virus) and by reverse transcriptase – polymerase chain reaction (RT-PCR)
3. Determining if dose correlates with incidence/duration of ZIKV in blood, urine, cervico-vaginal secretions, semen, and saliva

A suitable ZIKV strain for CHIM studies is defined as one in which:

1. $\geq 80\%$ of ZIKV or DENV-naïve inoculated subjects develop detectable viremia, as determined by direct virus culture **and**
2. Infectious virus is detected on more than 1 day for $\geq 80\%$ of subjects with detectable viremia **and**
3. The geometric mean peak titer of virus recovered by culture is $2.0 - 3.0 \log_{10}$ PFU/mL

Ideally, the ZIKV strain would also induce one or more of the following clinical signs in $\geq 50\%$ of infected subjects, however this will not be included in dose escalation criteria.

- a) Fever
- b) Rash
- c) Non-purulent conjunctivitis
- d) Myalgia
- e) Arthralgia

Secondary Study Objectives:

1. Characterize the clinical presentation of acute ZIKV infection by assessing the frequency of adverse events (AEs), graded by severity, occurring within 28 days of ZIKV administration
2. Longitudinal analysis of virus present in blood, urine, saliva, cervico-vaginal secretions, and semen
3. Time course of the neutralizing antibody response to ZIKV infection

Exploratory Objectives:

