1.3.2.3 ZIKV-SJRP (Cohort 1)

ZIKV-SJRP or placebo was administered to 14 women in cohort 1 randomized 5:2 in 2 blocks of volunteers. Ten women received ZIKV-SJRP and 4 women received placebo. Adverse events following administration of ZIKV-SJRP or placebo are shown in Table 4. ZIKV-like rash was observed in 9/10 volunteers who received ZIKV-SJRP and was the most common adverse event related to ZIKV-administration. Non-purulent conjunctivitis occurred in 50% of ZIKV-SJRP recipients, arthralgia in 70% and myalgia in 50%. Fever was not observed nor were any signs or symptoms consistent with GBS.

ZIKV-SJRP was recovered from 100% of those who received the virus. Both infectious virus and virus detected by PCR were recovered from the serum of all 10 infected volunteers (Figure 5). The virus detected by PCR was below the cut-off for discharge from the inpatient unit at all times post-administration. Infectious virus titer peaked at day 5 in 6/10 volunteers. The mean peak titer was 46.8 PFU/mL (1.67 \log_{10} PFU/mL). Peak virus titer was below 100 PFU/mL (2 \log_{10} PFU/mL) in 8/10 volunteers and below 1,000 PFU/mL (3 \log_{10} PFU/mL) in the remaining 2 volunteers. Infectious ZIKV-SJRP was found infrequently in CVS, saliva, and urine (Table 5). ZIKV-SJRP was found by qPCR in urine, saliva, and CVS in 80%, 70%, and 50% of women, although the titers were low and the duration of shedding short (Table 5). ZIKV-SJRP was not recovered from any specimen taken from placebo recipients. The low peak titer following inoculation with 100 PFU of ZIKV-SJRP suggests that challenge studies may be safely performed in an outpatient setting.

Table 4: All Adverse Events Following One Dose of Cohort 1 (ZIKV-SJRP/placebo) (CIR 316)

	ZIKV-SJRP (n=10) N (%)	Placebo (n=4) N (%)	P value (1-sided) ¹
Local			
Erythema	1 (10.0%)	0 (0.0%)	0.7143
Tenderness	1 (10.0%)	0 (0.0%)	0.7143
Pain	0 (0.0%)	0 (0.0%)	n/a
Pruritus	0 (0.0%)	0 (0.0%)	n/a
Induration	0 (0.0%)	0 (0.0%)	n/a
Systemic			
Fever	0 (0.0%)	0 (0.0%)	n/a
Headache	9 (90.0%)	3 (75.0%)	0.9341
Zika-like Rash	9 (90.0%)	0 (0.0%)	0.0050
Neutropenia ²	1 (10.0%)	0 (0.0%)	0.7143

	ZIKV-SJRP (n=10) N (%)	Placebo (n=4) N (%)	P value (1-sided) ¹
Nonpurulent conjunctivitis	5 (50.0%)	0 (0.0%)	0.1259
Elevated ALT	0 (0.0%)	1 (25.0%)	1.0000
Myalgia	5 (50.0%)	0 (0.0%)	0.1259
Arthralgia	7 (70.0%)	0 (0.0%)	0.0350
Retro-orbital Pain	4 (40.0%)	0 (0.0%)	0.7203
Fatigue	5 (50.0%)	2 (50.0%)	0.4286
Muscle weakness	1 ³ (10.0%)	0 (0.0%)	0.7143

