Prolonged PT	0 (0.0%)	0 (0.0%)	n/a
Hyporeflexia	0 (0.0%)	0 (0.0%)	n/a
Prolonged PTT	0 (0.0%)	0 (0.0%)	n/a
Thrombocytopenia	0 (0.0%)	0 (0.0%)	n/a

1. Greater for ZIKV-SJRP

2. Neutropenia was defined as an ANC $\leq 1,000/\text{mm}^3$.

3. Muscle weakness was reported by the volunteer but was not detected on physical examination. It lasted 1 day.

[figure not shown]

Figure 5: Kinetics of ZIKV-SJRP in Serum by Culture and Quantitative PCR

Table 5: Recovery of ZIKV-SJRP from Serum, Whole Blood, CVS, Saliva, and Urine
ZIKV-SJRP recovered by virus culture (infectious virus) (Day 0 – 28)

Sample	Frequency (N=10)	Mean peak titer (\log_{10} PFU/mL)	Mean day of onset	Mean duration (days)	Duration range (days)
Serum	100%	1.67	4.0	4.7	4 - 6
Whole blood	40%	1.7	5.3	2.3	1 - 3
CVS	10%	2.30	10.0	1.0	1 - 1
Saliva	30%	0.50	8.7	1.0	1 - 1
Urine	10%	0.7	10.0	3.0	3 - 3
ZIKV-SJRP recovered by quantitative PCR (Day 0 – 28)					
Serum	100%	5.11	2.5	7.5	7 - 10
Whole blood	100%	4.19	4.2	7.8	4 - 15
CVS	50%	2.72	10.7	3.8	1 - 7
Saliva	70%	2.69	10.3	1.9	1 - 5
Urine	80%	3.00	11.5	3.4	1 - 10

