3. Obtain approximately 15 mL of blood for virus isolation from serum and whole blood (PCR and culture) and PAXGene.

Study Day 2

1. Perform interim history and focused physical exam, concentrating on any acute complaints.
2. Record vital signs twice a day.
3. Obtain approximately 15 mL of blood for virus isolation from serum and whole blood (PCR and culture).
4. Obtain clean-catch urine for virus isolation (PCR/culture).
5. Obtain saliva sample for virus isolation (PCR/culture).
6. Obtain 2 mL of blood for PAXGene.

Study Day 3

1. Perform interim history and focused physical exam, concentrating on any acute complaints.
2. Record vital signs twice a day.
3. Obtain approximately 15 mL of blood for virus isolation from serum and whole blood (PCR and culture) and PAXGene.

Study Day 4

1. Perform interim history and focused physical exam, concentrating on any acute complaints.
2. Record vital signs twice a day.

3. Obtain approximately 47 mL of blood for CBC with differential, virus isolation from serum and whole blood (PCR/culture), immunology (serum, plasma, PBMCs), and PAXGene.
4. Obtain clean-catch urine for virus isolation (PCR/culture).
5. Obtain cervico-vaginal secretion or semen sample for virus isolation (PCR/culture).
6. Obtain saliva sample for virus isolation (culture/PCR).
7. Obtain oral fluid for serology (CIR site only).

Study Day 5

1. Perform interim history and focused physical exam, concentrating on any acute complaints.
2. Record vital signs twice a day.
3. Obtain 13 mL of blood for virus isolation from serum and whole blood (PCR/culture).
4. Cohorts 3 and 4: Perform mosquito feeding on subset of volunteers.

Study Day 6

1. Perform interim history and focused physical exam, concentrating on any acute complaints.
2. Record vital signs twice a day.
3. Obtain approximately 15 mL of blood for virus isolation from serum and whole blood (culture/PCR) and PAXGene.
4. Obtain clean-catch urine for virus isolation (PCR/culture).
5. Obtain saliva sample for virus isolation (PCR/culture).
6. Obtain oral fluid for serology (CIR site only).
7. Cohorts 3 and 4: Perform mosquito feeding on subset of volunteers.

Study Day 7

1. Perform interim history and focused physical exam, concentrating on any acute complaints.
2. Record vital signs twice a day.
3. Obtain 13 mL of blood for virus isolation from serum and whole blood (PCR/culture).
4. Cohorts 3 and 4: Perform mosquito feeding on subset of volunteers.

Study Day 8

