3. Obtain approximately 22 mL of blood for CBC with differential, AST, ALT, serum creatinine, virus isolation from serum and whole blood (PCR/culture), and PAXGene.

4. Obtain clean-catch urine for virus isolation (PCR/culture).
5. Obtain cervico-vaginal secretion or semen sample for virus isolation (PCR/culture).
6. Obtain saliva sample for virus isolation (PCR/culture).
7. Obtain oral fluid for serology (CIR site only).
8. Perform serum β -HCG testing (females only).
9. Review pregnancy prevention and continued use of barrier contraceptives.

Study Day 14 (\pm 1 day from 14 days following test article administration)

1. Perform interim history, including sexual history, and focused physical exam, concentrating on any acute complaints.
2. Record vital signs from subject diary card and perform vital signs.
3. Obtain approximately 45 mL of blood for immunology (serum, plasma, PBMCs), PAXGene, and virus isolation from serum and whole blood (PCR/culture).
4. Obtain clean-catch urine for virus isolation (PCR/culture).
5. Obtain cervico-vaginal secretion sample for virus isolation (PCR/culture).
6. Obtain saliva sample for virus isolation (PCR/culture).
7. Obtain oral fluid for serology (CIR site only).
8. Perform serum β -HCG testing (females only).
9. Review pregnancy prevention and continued use of barrier contraceptives.

Study Day 16 (\pm 1 day from 16 days following test article administration)

1. Perform interim history, including sexual history, and focused physical exam, concentrating on any acute complaints.
2. Record vital signs from subject diary card and perform vital signs.
3. Obtain approximately 22 mL of blood for CBC with differential, AST, ALT, serum creatinine, virus isolation from serum and whole blood (PCR/culture), and PAXGene.
4. Perform serum β -HCG testing (females only).
5. Obtain clean-catch urine for virus isolation (PCR/culture).
6. Obtain cervico-vaginal secretion or semen sample for virus isolation (PCR/culture). (Cervico-vaginal cup may be inserted at home by the volunteer prior to presentation to the clinic).
7. Obtain saliva sample for virus isolation (PCR/culture).
8. Obtain oral fluid for serology (CIR site only).
9. Review pregnancy prevention and continued use of barrier contraceptives.

Study Day 21 (\pm 1 day from 21 days following test article administration)

1. Perform interim history, including sexual history, and focused physical exam, concentrating on any acute complaints.

2. Record vital signs.

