The study is powered to detect a difference in the occurrence of virus in blood, urine, cervico-vaginal secretions, or saliva following administration of one of 2 ZIKV at different doses, compared with placebo recipients. A sample size of 10 ZIKV recipients and 4 placebo recipients will be able to detect a statistically significant difference ($\alpha = 0.05$) in recovery of infectious ZIKV from the blood between the ZIKV and placebo groups at a power of 0.99 with $\geq 80\%$ of ZIKV-inoculated subjects having detectable ZIKV viremia and 0 placebo recipients having detectable ZIKV in blood and body secretions. The detection of ZIKV by RT-PCR and by virus culture from blood, urine, cervico-vaginal fluids, semen and saliva in recipients of each ZIKV strain will be compared to placebo recipients. In addition, the magnitude and duration of ZIKV presence in blood, urine, cervico-vaginal secretions, semen and saliva will be compared to one another at each dosing level. The effect of dose escalation on the presence of virus in blood, urine, saliva, cervico-vaginal secretions and semen will also be evaluated. Multiple comparisons analysis will be used to compare the magnitude and duration of virus presence at each dose level of each candidate ZIKV and placebo recipients.

Measuring the transmissibility of ZIKV-SJRP and ZIKV-Nicaragua from infected volunteers to mosquitoes is an exploratory endpoint. Following feeding on volunteers, mosquitoes will be returned to the NIH for analysis (Section 6.7). The heads and thoraces of the mosquitoes will be examined for ZIKV antigen. If antigen is detected in the head of the mosquitoes, it will be assumed that the virus escaped the mid-gut barrier and is present in the salivary glands.

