9.5.2 Virology

Subjects who were enrolled through Study Day 180, even if they missed one or more visits during this time period will be included in the per-protocol analysis of viral shedding. Because there are frequent visits and an inpatient stay, missing these time-points is not expected to affect the analysis of the duration of virus shedding.

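### Shedding duration is undefined and compared between fluids sampled on different days, so short episodes score shorter in sparsely sampled fluids, semen most of all

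*Combined protocol and SAP*

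**What the plan says.** Duration by fluid is part of the primary objective in the Protocol Precis: "Determining the quantity and duration of ZIKV in blood, urine, cervico-vaginal secretions, semen, and saliva by culture" and by RT-PCR. Sections 2.1 and 2.2 repeat it. Section 9.2 then states, for every dose separately, that "the magnitude and duration of ZIKV presence in blood, urine, cervico-vaginal secretions, semen and saliva will be compared to one another". The methods named there are summary statistics, t-tests, linear regression and an unspecified multiple-comparisons analysis. No section says how duration is calculated or how gaps between samples are treated.

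Section 6.4.1.2 sets the sampling days. On shared genital-sampling days the instruction is "Obtain cervico-vaginal secretion or semen sample for virus isolation (PCR/culture"); on Days 10 and 14 only CVS is collected.

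Table 5 (Section 1.3.2.3) gives culture durations for ZIKV-SJRP of 1.0 day (range 1 to 1) in saliva, 1.0 day (1 to 1) in CVS and 3.0 days (3 to 3) in urine. The text describes qPCR findings in urine, saliva and CVS with the remark "although the titers were low and the duration of shedding short (Table 5").

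On gaps, the only comment is in Section 9.5.2, about missed visits: "missing these time-points is not expected to affect the analysis of the duration of virus shedding".

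**The concern.** A duration built only from positive samples depends on how often samples were taken as well as on how long virus was present. When fluids with different schedules are compared directly, part of the difference comes from the schedule.

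Semen is the most exposed. Sections 1.1 and 4 say men are enrolled to measure infectious virus in semen and so inform the risk of male-to-female transmission, yet semen has the widest gaps. The bias makes semen shedding look brief, which is the reassuring direction. Section 9.5.2 rests on frequent visits and the inpatient stay, but only two post-dose semen samples (Days 4 and 8) fall within that stay.

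**Working it through.** **Sampling days (Section 6.4.1.2, nominal days)**

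- Blood: 0 to 10 daily, 12, 14, 16
- Urine and saliva: 0, 2, 4, 6, 8, 10, 12, 14, 16
- CVS: 0, 4, 8, 10, 12, 14, 16
- Semen: 0, 4, 8, 12, 16
- All fluids: then 21, 28 and later. Blood is tested at Day 21, and all fluids from Day 28, only under stated conditions.

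**Which rule gives the Table 5 figures?** Two rules fit the three culture durations: span (last positive day − first positive day + 1) and a count of positive samples. For urine, positives on Days 10 and 12 give a span of 12 − 10 + 1 = 3. Plain last minus first does not fit, because a lone positive would score 0. Span is more plausible. The urine qPCR maximum of 10 arises as 21 − 12 + 1, whereas a count of 10 would need every post-dose urine sample through Day 28 to be positive. A single positive scores 1 day under either rule.

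**What a lone positive shows.** Upper bound = next sampling day − previous sampling day, assuming both neighbouring samples are tested and negative.

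| Fluid | Upper bound in days (day of the lone positive) |
|---|---|
| Blood | 2 (Days 1-9), 3 (10), 4 (12, 14), 7 (16), 12 (21) |
| Urine, saliva | 4 (Days 2-14), 7 (16), 12 (21) |
| CVS | 8 (Day 4), 6 (8), 4 (10-14), 7 (16), 12 (21) |
| Semen | 8 (Days 4, 8, 12), 9 (16), 12 (21) |

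The CVS culture positive in Table 5 has onset Day 10, so its 1.0 day means under 12 − 8 = 4 days. The urine value of 3.0 means between 12 − 10 = 2 and 14 − 8 = 6 days if positives fell on Days 10 and 12.

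**Missed visit.** A lone semen positive on Day 8 is bounded by 12 − 4 = 8 days. If Day 12 is missed, the bound is 16 − 4 = 12 days.

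**Size of the bias (illustration).** Assumptions: span rule, perfect assay, every scheduled sample tested, onset uniform over the days shown. The onset ranges are not document values.

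| True duration, onset | Blood | Urine/saliva | CVS | Semen |
|---|---|---|---|---|
| 5 days, Days 6-14 | 4.0 | 3.75 | 3.75 | 2.0 |
| 5 days, Days 4-8 | 4.75 | 4.0 | 3.0 | 2.0 |
| 10 days, Days 4-8 | 9.5 | 9.0 | 8.0 | 7.0 |

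The semen value in the first row can be checked by hand. A 5-day episode catches two semen samples only if onset falls in Days 7-8 (samples 8 and 12) or Days 11-12 (samples 12 and 16). That is 2 of 8 onset days, or 25%, so the mean is 0.75 × 1 + 0.25 × 5 = 2.0 and 75% score 1 day. A true 3-day episode on a 4-day grid is missed 1 − 3/4 = 25% of the time. With a 10-day episode and onset over Days 6-14, blood scores 8.1 and semen 6.9. Under a count rule, the 5-day episode with onset over Days 6-14 scores 2.9 in blood and 1.25 in semen.

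**Testing rules for late samples.** The Day 28, 35, 56 and 70 footnotes in Section 6.4.1.2 make virology on every fluid conditional on earlier positive blood. The note closing that section makes testing from Day 21 conditional on the sample itself having been positive earlier. Under the footnotes, a man with positive semen but negative blood at Day 21 has no tested Day 28 semen result. His episode then has no upper bound, and the 12 days above does not apply.

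**The case against.** The strongest reply is that little depends on this. Section 9.2 calls the study exploratory. Suitability (Section 2.1), enrolment of the second block (Section 3.1.2.2) and the DSMB criteria (Section 7.6.3) use infectious virus, not duration in urine, saliva, CVS or semen. The low-risk statements rest mainly on how often infectious virus was recovered, and the outpatient suggestion in Section 1.3.2.3 rests on low peak titer. All of that stands. A reader might infer that the bias feeds a go/no-go rule; the documents do not support that.

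A reader might also conclude that no fluids, and neither sex, can be compared. That goes too far. One schedule serves all four cohorts, so blood, urine and saliva are sampled on the same days in women and men, and urine and saliva share a schedule.

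It is also fair that the scoring rule is inferred from Table 5, that the illustration depends on assumed onset, and that the bias is proportionally small for long episodes; Section 1.1 cites semen RNA persisting for 2 to 6 months. Finally, interval-censored modelling of the culture data in Table 5 (1 CVS, 1 urine and 3 saliva positives among 10 women) would add little to a listing.

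None of this supplies a definition for a measure named in the primary objective, or removes the bias from the comparisons that Section 9.2 announces.

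**Conclusion.** The concern holds in a limited form. Duration is undefined, and direct comparison of blood with other fluids, or of CVS or semen with the rest or with each other, is biased by unequal sampling. Semen scores shortest in the cases worked above. The effect is large for short episodes (2.0 days in semen against 4.0 to 4.75 in blood for a true 5 days) and modest for longer ones (6.9 to 7.0 against 8.1 to 9.5 for a true 10 days). Urine against saliva, and blood, urine or saliva across sexes, are unaffected.

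The upper bounds rest on nominal visit days and on the neighbouring samples being tested; visit windows shift them slightly. The mean scores rest on the assumed onset ranges, a perfect assay and the inferred span rule. That a lone positive scores 1 day holds under either candidate rule. No decision rule in the protocol is shown to be affected; what is at risk is the description of shedding, above all in semen.

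**What to change.** 1. In Section 9.2, define duration per subject and fluid by two bounds. The lower is first to last positive sample; the upper is last negative before to first negative after, right-censored if no later sample was tested.
2. Report both bounds, as a listing where positives are few and with an interval-censored estimate where numbers allow.
3. Compare fluids only on the sampling days they share. Days 0, 4, 8, 12, 16 and 21 are common to all five; Day 21 blood is tested only after a Day 16 positive, and the analysis should say how untested samples are handled.
4. Qualify Section 9.5.2 so that a missed visit widens the interval.
5. Reconcile the Section 6.4.1.2 visit footnotes with the note that closes the section, because they determine whether the end of semen shedding is observed.

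The cost is wording and re-tabulation, with no added sampling visits. Cohorts 3 and 4 are described as still to come, so the definition can be fixed before semen is analysed. The downsides are that stated durations become wider and less favourable, and that common-day comparisons set aside some blood, urine, saliva and CVS samples.

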OCRPRO	Office of Clinical Research Policy and Regulatory Operations
OR	odds-ratio
PAHO	Pan American Health Organization
PBMC	peripheral blood mononuclear cell
PCR	polymerase chain reaction
PFU	plaque-forming units
PHEIC	Public Health Emergency of International Concern
PI	principal investigator
PRNT ₅₀	50% plaque reduction neutralization titer
PT/PTT	prothrombin time/ partial thromboplastin time
RNA	ribonucleic acid
ROP	retro-orbital pain
RT-PCR	reverse transcriptase polymerase chain reaction
SAE	serious adverse event
SD	standard deviation
SE	standard error
SJRP	São José do Rio Preto, Brazil

SOP	standard operating procedure
SRCP	Safety Review and Communications Plan
SUSAR	serious and unexpected suspected adverse reaction
T _{max}	maximum temperature
TORO	transfer of regulatory obligations
ULN	upper limit of normal
WBC	white blood cell count
WHO	World Health Organization
Wt	wild-type
ZIKV	Zika virus
ZIKV-SJRP	Zika virus- São José do Rio Preto, Brazil

PROTOCOL PRECIS

Protocol Title: Phase I evaluation of two Zika viruses for use in controlled human infection models (CHIM)

Version: 10.0

Version Date: 07 June 2024

Version History:

- v9.0 01 December 2023
- v8.0 01 August 2023
- v7.0 20 February 2023
- v6.0 24 January 2023
- v5.0 14 June 2022
- v4.0 17 September 2021
- v3.0 13 August 2021
- v2.0 23 June 2021
- v1.0 31 July 2019

Phase: Phase 1

Principal Investigator [name]
Center for Immunization Research (CIR)
Johns Hopkins School of Public Health
[name]
Baltimore, MD 21205
[contact] (phone)

Co -investigator [name]
University of Vermont, College of Medicine
[name]
[name]
Burlington, VT 05405
[contact] (phone)

Subjects: Healthy male and non-pregnant female subjects between 18 - 40 years of age, inclusive, with no history of previous ZIKV or DENV infection.

No. of Subjects: Up to 56

Study Type: Randomized, placebo-controlled, double-blind

Duration: Subjects will be followed for approximately 26 weeks (approximately 180 days) from the time of inoculation. Subjects will be screened for eligibility up to 60 days prior to inoculation on Study Day 0.

Dose Escalation Schedule:

Cohort	No. of Subjects ¹	Sex	Dose	Virus
1	14	Female	10 ² PFU	ZIKV-SJRP/2016-184
2	14	Female	10 ² PFU	ZIKV-Nicaragua/2016
3 ²	14	Male	10 ² PFU	ZIKV-SJRP/2016-184
4 ²	14	Male	10 ² PFU	ZIKV-Nicaragua/2016

PFU = plaque-forming units, ZIKV-SJRP = Zika virus-São José do Rio Preto, Brazil

1. Virus:Placebo ratio, 5:2

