3.1.2 Study Design

This study will include 4 cohorts of 14 ZIKV and DENV-naïve female and male subjects, 18 - 40 years of age (total: up to 56 subjects). Within each cohort, 10 subjects will receive ZIKV and 4 subjects will receive a placebo on Study Day 0. Cohorts 1 and 2 (Dose = 10^2 PFU) will be enrolled first and will enroll only women. Cohorts 3 and 4 (Dose = 10^2 PFU) will enroll men.

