3.1.3 Sample Size and Placebo Ratio Primary Study

Fourteen subjects (10 ZIKV and 4 placebo recipients) will be enrolled into each dose cohort. This sample size was chosen based on our experience in developing the DENV-2 CHIM (CIR286, clinical trials.gov NCT01931176, [47]) and the DENV-3 CHIM (CIR304, clinical trials.gov NCT02684383).

Ten subjects are chosen to receive each ZIKV strain at each dose for the following reasons:

- A sample size of 10 ZIKV recipients and 4 placebo recipients in each cohort will be able to detect a statistically significant difference ($\alpha = 0.05$) in recovery of infectious ZIKV from the blood between the 10 ZIKV recipients and 4 placebo recipients at a power of 0.99 with $\geq 80\%$ of ZIKV-inoculated subjects having detectable ZIKV viremia and none of the placebo recipients having detectable viremia.

- A sample size of 10 ZIKV recipients and 4 placebo recipients in each cohort will be able to detect a statistically significant difference ($\alpha = 0.05$) in any clinical sign between the 2 groups at a power of 0.71 if the clinical sign occurs in $\geq 80\%$ of ZIKV recipients and occurs in ≤ 1 placebo recipients. We have included placebo-recipients so that we can determine if common AEs are ZIKV-related.

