9.2 Statistical Methods

This study, like other Phase 1 studies, is exploratory rather than confirmatory. As such, the primary analyses will assess frequencies of adverse events and describe patterns of challenge virus replication and immune response within individuals at multiple timepoints (e.g. pre vs post challenge), and within and between groups (challenge virus vs. placebo).

Continuous outcomes (e.g. peak titer of virus shed, antibody titers over time) will be presented with the use of summary statistics such as means, medians, quartiles, ranges, etc. as appropriate, with data displayed in both tables and figures. Student’s T-tests and linear regression will be used to assess differences in continuous outcomes between subjects in each study arm. Correlations between 2 continuous outcomes will be evaluated with the use of Pearson or Spearman correlation coefficients and graphed as scatterplots.

Proportions of subjects with dichotomous outcomes of interest (e.g. presence or absence of: specific AEs, viral shedding, seropositivity, four-fold rise in antibody response, etc.) observed in each group will be summarized in tables and figures. Differences in proportions between groups will be compared with χ^2 tests, Fisher's exact tests, and logistic regression as appropriate. Outcomes will be summarized by severity and/or category where applicable (e.g. immediate, systemic, local AE).

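### Section 9.2 puts placebo recipients, whose virus titer and duration do not vary, into the multiple-comparisons analysis of magnitude and duration; depending on the unnamed procedure, this can distort strain-versus-strain contrasts.

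*Combined protocol and SAP*

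**What the plan says.** Section 9.2 (Statistical Methods) says of continuous outcomes, with peak titer as one of its examples, that Student's "T-tests and linear regression will be used to assess differences in continuous outcomes between subjects in each study arm". It adds that magnitude and duration of virus in the body fluids "will be compared to one another at each dosing level", and that a multiple-comparisons analysis will "compare the magnitude and duration of virus presence at each dose level of each candidate ZIKV and placebo recipients". It does not name the procedure, the family of comparisons, the variance model or the value given to undetectable virus, and it does not say whether placebo recipients are pooled over cohorts.

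On group sizes, Section 3.1.2 states: "Within each cohort, 10 subjects will receive ZIKV and 4 subjects will receive a placebo on Study Day 0".

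On placebo outcomes, the sizing in Section 3.1.3 assumes "none of the placebo recipients having detectable viremia", and Section 9.2 repeats the assumption as "0 placebo recipients having detectable ZIKV in blood and body secretions". Section 1.3.2.3 reports for cohort 1 that "ZIKV-SJRP was not recovered from any specimen taken from placebo recipients". Section 9.2 also plans a separate comparison of virus detection between each strain and placebo, and describes the study as exploratory.

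**The concern.** A placebo recipient's peak titer and duration of shedding are known in advance: zero, or a fixed value such as the detection limit on a log scale. Either way the group has no variance. Whether virus appears in placebo recipients at all is a question of occurrence, which Section 9.2 already covers. Within the magnitude and duration family, only contrasts between active groups are open questions.

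Including the constant group can affect those contrasts in two ways.

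- **Variance.** Ordinary linear regression, one of the two named methods, assumes a common residual variance. A constant arm adds residual degrees of freedom but no sum of squares, so the variance used to judge the strain contrast is too small.
- **Multiplicity.** If each pair is tested separately and adjusted, the strain contrast may pay for placebo comparisons whose answer is already known.

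Magnitude and duration in blood, urine, saliva, cervico-vaginal secretions and semen are part of the primary and secondary objectives (Sections 2.1 and 2.2). Their intervals should be valid even in an exploratory study.

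**Working it through.** **The plan's own figure.** Section 9.2 gives no figure for the magnitude or duration contrasts. Its one power figure concerns occurrence: 0.99 for 10 ZIKV recipients at 80% against 4 placebos at 0%. A one-sided normal approximation with pooled null variance reproduces it. The pooled proportion is 8/14 = 0.571, the null SE is sqrt(0.571 × 0.429 × (1/10 + 1/4)) = 0.293, and the alternative SE is sqrt(0.8 × 0.2/10) = 0.126. Then (0.8 − 1.645 × 0.293)/0.126 = 2.52, giving power 0.994. The rest of this check does not depend on it.

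**Inputs.** Each cohort has 10 ZIKV and 4 placebo recipients (Section 3.1.2). Two cohorts, one per strain, give 10/10/8 with placebo pooled; all four give 20/20/16. Placebo variance is 0. Assumptions: equal SD in the two strains, two-sided alpha 0.05.

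**1. Common-variance regression, unadjusted strain contrast.** The estimated residual variance is scaled by (active df)/(total residual df) = (n1 + n2 − 2)/(n1 + n2 − 2 + n0 − 1).

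| Layout | Variance ratio | SE ratio | Effective critical value | True type I error |
|---|---|---|---|---|
| 10/10/8 | 18/25 = 0.720 | 0.849 | 2.060 × 0.849 = 1.748 on 18 df | 0.098 |
| 10/10/4 | 18/21 = 0.857 | 0.926 | 2.080 × 0.926 = 1.925 on 18 df | 0.070 |
| 20/20/16 | 38/53 = 0.717 | 0.847 | 2.006 × 0.847 = 1.698 on 38 df | 0.098 |

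Simulation with 200,000 runs gave 0.097, 0.070 and 0.097. At 10/10/8 the SE is 15% too small, and the 95% interval is 1.748/2.101 = 0.832 of its correct width.

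**2. Tukey, four cohorts of 10 plus 16 pooled placebos.** The variance ratio is 36/51 = 0.706 and the SE ratio 0.840. The studentized-range critical value for five groups on 51 df is 3.999, and 3.999 × 0.840 = 3.360. Referred to four groups on 36 df, this gives a familywise error of 0.100 among the active cohorts.

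**3. Bonferroni over three two-group t-tests.** A two-group t-test of one strain against the other does not use the placebo data, so its SE is correct, but it is run at 0.05/3 = 0.0167. With 10 against 10 and a 1 SD difference (noncentrality 1 × sqrt(10/2) = 2.236, 18 df), power is 0.56 at 0.05 and 0.37 at 0.0167.

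**4. Procedures that leave the contrast essentially unharmed.**

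- Three-arm Tukey at 10/10/8: critical value 2.491 × 0.849 = 2.114 on 18 df, error 0.049. The two effects nearly cancel.
- Bonferroni on the pooled regression at 10/10/8: 2.566 × 0.849 = 2.177, error 0.043.
- Holm with two-group t-tests: the placebo comparisons are rejected first, so the strain contrast is tested at close to full alpha. Simulated error is 0.048 to 0.050.

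**5. Does it matter for peak serum titer?** Section 1.3.2.4 gives 3.63 against 1.67 log10 PFU/mL, a difference of 1.96, with 5 and 10 recipients. No SD is given. The dengue challenge SEs in Table 3 imply 0.07 × sqrt(57) = 0.53 and 0.15 × sqrt(10) = 0.47. Assuming a range of 0.3 to 1.0, the worst case is t = 1.96/(1.0 × sqrt(1/10 + 1/5)) = 3.58 on 13 df, p = 0.0034. Tripled for Bonferroni, that is about 0.010. The difference stands either way.

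**The case against.** The strongest reply is that Section 9.2 commits to none of the harmful procedures.

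- The sentence that brings in placebo groups subjects by strain and dose level. All four cohorts now receive the same dose, so its natural reading is three arms, and three-arm Tukey holds the error at 0.049. The four-cohort layout with pooled placebos is not specified.
- The 15% and 0.098 need an unadjusted regression contrast with placebo pooled over cohorts, whereas the sentence concerns an adjusted analysis. The other named method, a two-group Student's t, is untouched by placebo.
- The strain contrast is itself inferred. The sentence could mean each strain against placebo only, and the comparison of groups with one another may refer to body fluids.

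All of this stands, and it limits the point to what can happen under choices the plan leaves open. It does not make the analysis set sound. Three-arm Tukey works because two errors offset each other, and Holm works only if each test uses its own two groups. If placebo is compared only with each strain, comparing magnitude with a constant still adds little to the occurrence comparison.

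A reader might also infer that the flaw drives strain selection. The documents do not support that. The suitability criteria in Sections 2.1 and 7.6.3 are per-strain thresholds and use no between-strain p-value or interval. The transmissibility reasoning rests on titers set against about 3 log10 PFU/mL and on direct mosquito feeding. Section 9.2 calls the study exploratory.

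**Conclusion.** The point holds in a conditional form. Section 9.2 includes a group with no variance in the comparison of virus magnitude and duration, which breaks the equal-variance assumption of ordinary regression, and it leaves open the choices that decide whether this matters. Across the procedures checked for two strains of 10, the type I error of the strain contrast runs from 0.0167 (Bonferroni, two-group t-tests) to 0.098 (unadjusted regression with 8 pooled placebos), with some ordinary procedures close to 0.05. These figures assume equal SDs in the two strains and constant placebo values.

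A reader might infer that, as written, the strain contrast must be either anti-conservative or underpowered. That goes too far: three-arm Tukey and Holm with two-group t-tests do neither appreciable harm.

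The peak serum titer difference and the suitability thresholds are not affected. Closer contrasts could be. Mean duration of infectious virus in serum is 4.7 days for SJRP (Table 5) and appears to be 5.4 for Nicaragua (Table 7, where the columns do not line up with their headings). Semen shedding will come from cohorts 3 and 4 only. This is a free improvement to an exploratory plan and does not threaten its main conclusions.

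**What to change.** In Section 9.2, replace the multiple-comparisons sentence with one saying that:

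- magnitude and duration of virus are compared between strains among ZIKV recipients only, by Welch's t-test or a permutation test;
- any multiplicity adjustment is named and applies to those contrasts alone;
- ZIKV and placebo recipients are compared on occurrence of virus only, as the section already plans.

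Placebo titers and durations can still be listed descriptively. The cost is about one sentence of text, with no new subjects, samples or procedures.
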